### 5.3.2 Handling of Participant Withdrawals or Termination

All patients, except those who withdraw consent, will be followed up according to the study procedures. Subjects should be encouraged to continue participation in the trial until determination of disease progression. Those who discontinue study therapy before progression should allow the collection of necessary laboratory results until disease progression criteria are fulfilled. If the study drug is discontinued prior to disease progression, the reason for the discontinuation must be documented in the eCRF.

If lost to follow-up, the investigator should contact the patient or a relative by telephone followed by registered mail or through a personal visit to establish as completely as possible the reason for the withdrawal.

## 5.4 Premature Termination or Suspension of Study

The study can be terminated for any reason and at any time by the Sponsor. Should this be necessary, the patient should be seen as soon as possible and treated as a prematurely withdrawn patient. All measures will be adopted to ensure the safeguarding of the patient's interests.

## 6. Study Treatment

### 6.1 Study treatments and Control Description

#### 6.1.1 Formulation, Appearance, Packaging, and Labeling

This is an open-label study. Daratumumab is considered investigational treatment and will be supplied free of charge by the sponsor. Dexamethasone will be obtained by the Sponsor according to specific regulatory requirements. All study treatments used in this study, along with their packaging and labeling, have been approved by local Health Authorities.

Investigational Medicinal Products (IMP):

- Daratumumab (Darzalex®)

Daratumumab 20 mg/mL concentrate for solution for infusion. The solution is colorless to yellow.

Each 20 mL vial contains 400 mg of daratumumab (20 mg daratumumab per mL).

- Dexamethasone

Dexamethasone vials or tablets of various strengths and packaging configuration for oral administration.

#### 6.1.2 Product Storage and Stability

Investigational treatment must be received by a designated person at the study site, handled and stored safely and properly, and kept in a secured location to which only the investigator and designees have access. Upon receipt, all investigational treatment should be stored according to the instructions specified on the labels. Clinical supplies are to be dispensed only in accordance with the protocol. Medication labels will be in the local language and comply with the legal requirements of each country.

Daratumumab vials should be stored at 2°-8° C in its original package to protect from light.

After dilution, unless the method of opening/dilution precludes the risk of microbial contamination, the product should be used immediately. If not used immediately, in-use storage times and conditions are the responsibility of the user and should be no more than 24 hours at refrigerated conditions (2°-8° C) protected from light, followed by 15 hours (including infusion time) at room temperature (15°-25° C) and room light (see [Appendix 1](#)).

Dexamethasone does not require any special storage conditions.

#### 6.1.3 Preparation

Daratumumab is to be prepared according to the instructions in [Appendix 1](#).

## 6.1.4 Dosing and Administration

### Daratumumab

Daratumumab will be given at a dose of 16 mg/kg administered as an intravenous (IV) infusion at weekly intervals (QW) for 8 weeks, then every 2 weeks (Q2W) for an additional 16 weeks, then every 4 weeks (Q4W) thereafter.

See [Appendix 2](#) for guidelines for the intravenous infusion of daratumumab and for pre-infusion and post-infusion medications to be given to mitigate potential infusion reactions.

Infusion-related reactions (IRRs) have been reported in approximately half of all patients treated with daratumumab. Patients should therefore be monitored throughout the infusion and the post-infusion period. The majority of IRRs occurred at the first infusion and were Grade 1-2. Four percent of all patients had an IRR at more than one infusion. Severe reactions have occurred, including bronchospasm, hypoxia, dyspnoea, hypertension, laryngeal oedema and pulmonary oedema. Symptoms predominantly included nasal congestion, cough, throat irritation, chills, vomiting and nausea. Less common symptoms were wheezing, allergic rhinitis, pyrexia, chest discomfort, pruritus, and hypotension.

Patients should be pre-medicated with antihistamines, antipyretics and corticosteroids to reduce the risk of IRRs, as per local practice.

See the Summary of Product Characteristics for more details about daratumumab.

### Dexamethasone

The recommended dose of dexamethasone is 40 mg (20 mg for patients > 75 years of age) orally once daily on Days 1, 8, 15 and 22 of each 28-day treatment cycle. On the days that dexamethasone dosing is concurrent with the daratumumab administration, dexamethasone will be administered at a dose of 40 mg IV or PO prior to the daratumumab infusion (IV: approximately 1 hour before, PO: 1-3 hours before) and will serve as both the pre-medication and the therapeutic dose (i.e. no other corticosteroids can be administered as pre-medication on the days that dexamethasone dosing is concurrent).

See the Summary of Product Characteristics for more details about dexamethasone.

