### 4. Study Design and Study End points

#### 4.1 Description of the Study Design

This is a multicenter, Phase 2, single arm, open-label study evaluating daratumumab with dexamethasone (DaraD) in subjects with relapsed or refractory multiple myeloma who have received at least two prior lines of treatment, with both bortezomib- and lenalidomide-based regimens and have renal impairment.

Approximately 38 subjects located in approximately 5 centers in Greece and 2 centers in Italy will receive daratumumab with dexamethasone. Treatment cycles have a duration of 28 days:

**Daratumumab** will be given at a dose of 16 mg/kg administered as an intravenous (IV) infusion at weekly intervals (QW) for 8 weeks, then every 2 weeks (Q2W) for an additional 16 weeks, then every 4 weeks (Q4W) thereafter. Subjects will receive pre-infusion medications before infusions to mitigate potential infusion reactions.

**Dexamethasone** will be administered according to standard clinical practice and at a recommended total dose of 40 mg weekly (20 mg weekly for patients >75 years of age).

Subjects will receive treatment until disease progression or unacceptable toxicity.

Drug administration and follow-up visits will occur more frequently for early cycles (e.g., weekly or bi-weekly) (see *Table 7.2*). Disease evaluations will occur monthly and consist mainly of measurements of myeloma proteins and renal function indices. Other parameters may include bone

marrow examinations, skeletal surveys, assessment of extramedullary plasmacytomas, and measurements of serum calcium corrected for albumin, and  $\beta$ 2-microglobulin and albumin.

Assessment of myeloma response and disease progression will be conducted in accordance with the modified International Myeloma Working Group (IMWG) response criteria (see [Appendix 4](#)).

Assessment of renal response will be conducted in accordance with the International Myeloma Working Group (IMWG) response criteria (see Appendix 5).

Survival status and data of subsequent anti-myeloma treatment will be collected post-treatment.

The maximum duration of the study is of 37 months considering an accrual period of 24 months and a follow-up of the last patient of 13 months.

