### **Interruption of Missed Doses**

A daratumumab dose held for more than 3 days from the per-protocol administration date for any reason other than toxicities suspected to be related to daratumumab should be brought to the attention of the sponsor at the earliest possible time. Subjects missing  $\geq 3$  consecutive planned doses of daratumumab

for reasons other than toxicity should be withdrawn from treatment, unless, upon consultation with the sponsor and the review of safety and efficacy, continuation is agreed upon.

➤ Dexamethasone

Instructions for dose modifications of dexamethasone are shown in the table below:

Dyspepsia = Grade 1-2	Maintain dose and treat with histamine (H2) blockers or equivalent. Decrease by one dose level if symptoms persist.
Dyspepsia $\geq$ 3	Interrupt dose until symptoms are controlled. Add H2 blocker or equivalent and decrease one dose level when dose restarted.
Edema $\geq$ Grade 3	Use diuretics as needed and decrease dose by one dose level.
Confusion or mood alteration $\geq$ Grade 2	Interrupt dose until symptoms resolve. When dose restarted decrease dose by one dose level.
Muscle weakness $\geq$ Grade 2	Interrupt dose until muscle weakness $\leq$ Grade 1. Restart with dose decreased by one level.
Hyperglycemia $\geq$ Grade 3	Decrease dose by one dose level. Treat with insulin or oral hypoglycemic agents as needed
Acute pancreatitis	Discontinue patient from dexamethasone treatment regimen.
Other $\geq$ Grade 3 dexamethasone-related adverse events	Stop dexamethasone dosing until adverse event resolves to $\leq$ Grade 2. Resume with dose reduced by one level.

Dexamethasone dose reduction levels:

Dose reduction levels ( $\leq$  75 years of age): Starting dose 40 mg; dose level -1 20 mg; dose level-2 10 mg on Days 1, 8, 15 and 22 of each 28-day treatment cycle.

Dose reduction levels ( $>$  75 years of age): Starting dose 20 mg; dose level -1 12 mg; dose level-2 8 mg on Days 1, 8, 15 and 22 of each 28-day treatment cycle.

If recovery from toxicities is prolonged beyond 14 days, then the dose of dexamethasone will be decreased by one dose level.

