sPEP, uPEP 	X	X				X				X					X	X													
sIFE, uIFE 	X	X			X				X						X	X													
			To confirm CR regardless of whether measurable M-protein was present at baseline. See Section 7.1.1.1																										
sFLC assay, $\kappa/\lambda$ ratio 	X	X			X				X						X	X													
			Analyzed only when serum M-protein or urine M-protein or both assessed by PEP is/are non-measurable and to identify sCR in case CR criteria are met. See Section 7.1.1.2																										
Plasma cell count in bone marrow	X	Plasma cell count during the study as clinically indicated to qualify for CR and PD for patients with non-measurable disease by M protein in serum and urine as well as by FLC. See Section 7.1.1.3																											
MRD		As per institution's practice at complete response or better and thereafter every 6 months as long as CR/sCR is maintained through EuroFlow cytometry. See Section 7.1.1.6																											
Corrected calcium 	X	X			X				X						X	X													
Skeletal survey 	X	As clinically indicated; CT/MRI in case of newly symptomatic areas with no X-ray finding. See Section 7.1.1.6																											
Assessment of extramedullary soft tissue plasmacytoma	X	Clinical assessment on day one of each cycle at the End of treatment and at Post treatment follow-up every 4 weeks. CT or MRI at screening only if there are STP findings during the clinical assessment or documented evidence from previous imaging assessments and as clinically indicated. See Section 7.1.1.4																											
Response assessment by Investigator		C2D1			X				X						X	X													
Treatment																													
Daratumumab		X	X	X	X	X		X			X																		
Dexamethasone		X	X	X	X	X	X	X	X	X	X	X	X	X															
		40 mg (20 mg for patients > 75 years of age) orally, weekly																											

Day of Cycle (28-days)	Screening ^	Treatment: visit window during the treatment period is +/- 3 days												End of treatment EOT 	Post treatment FU Every 4 weeks 	Survival follow-up Every 12 weeks		
		Cycles 1 and 2				Cycles 3-6				Cycles 7 and beyond								
		-21 to 1	1 BL	8	15	22	1	8	15	22	1	8	15	22				
Other anti-neoplastic therapies		Not permitted												X	X	X		
Survival follow-up																X		

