### Recommended concomitant medications

#### Pre-infusion medication

Pre-infusion medications should be administered to reduce the risk of IRRs to all patients approximately 1-3 hour prior to every infusion of DARZALEX as follows:

- intravenous corticosteroid (dexamethasone 20 mg, methylprednisolone 100 mg, or equivalent dose of an intermediate-acting or long-acting corticosteroid) plus
- oral antipyretics (paracetamol 650 to 1,000 mg), plus
- oral or intravenous antihistamine (diphenhydramine 25 to 50 mg or equivalent).

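### Protocol Section 6.1.4 sets infusion-day dexamethasone at 40 mg for all ages, contradicting the 20 mg it gives patients over 75 everywhere else

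*Protocol*

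**What the plan says.** The dexamethasone part of Protocol Section 6.1.4 opens with the general rule, which covers four days of every cycle (Days 1, 8, 15 and 22): "The recommended dose of dexamethasone is 40 mg (20 mg for patients > 75 years of age) orally once daily". The next sentence covers days on which dexamethasone coincides with daratumumab. There, "dexamethasone will be administered at a dose of 40 mg IV or PO prior to the daratumumab infusion", and this dose "will serve as both the pre-medication and the therapeutic dose". No other corticosteroid may be given as pre-medication on those days. This second sentence carries no age exception.

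Four other places in the current Protocol give 20 mg for patients over 75:

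- The Protocol Summary, under the description of study treatment, repeats the general rule.
- Section 4.1 gives a "recommended total dose of 40 mg weekly (20 mg weekly for patients >75 years of age".
- Section 6.1.5, in the reduction levels for patients over 75, has "Starting dose 20 mg; dose level -1 12 mg; dose level-2 8 mg on Days 1, 8, 15 and 22".
- Table 7.2, in the dexamethasone row, has "40 mg (20 mg for patients > 75 years of age) orally, weekly".

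SAP version 1.0 also gives 20 mg for this group, in Sections 4, 6.1.2 and 6.2 and in Table 1. It is dated 02-02-2018 and so predates Protocol version 5.0 of June 2020.

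**The concern.** The infusion-day sentence is an instruction about what will be given, and it is more specific than the general rule before it. A careful reader could therefore let it govern on infusion days. In Cycles 1-2 daratumumab is weekly, so every dexamethasone day is an infusion day. A patient over 75 dosed by this sentence could never start at the 20 mg that Section 6.1.5 names as the starting dose.

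Two sites could then treat the same patient differently and each point to Protocol text in support. At stake is up to twice the intended steroid dose on infusion days for older patients, whose risks from dexamethasone (among them hyperglycemia, fluid retention, hypertension, psychosis and serious infection) are listed in Section 2.1. There is also a smaller reporting consequence. Section 10.4.6 plans relative dose intensity for each component by 28-day cycle, and the planned dose for a patient over 75 depends on which sentence is used.

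**Working it through.** The plan states no cumulative dexamethasone dose, so there is no figure to reproduce. The check compares the texts and then does the dose arithmetic.

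**Can the two sentences be reconciled?** One route would be to treat the 40 mg as pre-medication separate from the weekly therapeutic dose. The text closes that route, because the infusion-day dose is stated to be the therapeutic dose as well. Section 4.1 also recommends a weekly total of 20 mg for patients over 75, which cannot contain a 40 mg dose. The two sentences conflict for this group.

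**Can such patients enrol?** Yes. Section 5.1 sets a minimum age of 18 and no maximum, and Section 6.1.5 has a separate set of dose levels for patients over 75.

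**Inputs**

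- Dexamethasone days: 1, 8, 15 and 22, so four per 28-day cycle (Section 6.1.4).
- Daratumumab: "weekly intervals (QW) for 8 weeks, then every 2 weeks (Q2W) for an additional 16 weeks", then every 4 weeks (Section 6.1.4). Infusions therefore fall on 4 of the 4 dexamethasone days in Cycles 1-2, 2 of 4 in Cycles 3-6, and 1 of 4 from Cycle 7, which agrees with Table 7.2.
- Patient over 75 at starting dose, with no reductions or missed doses.

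**Formulae, mg per cycle**, with k infusion days per cycle:

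- Age rule: 4 × 20 = 80.
- Infusion-day sentence read literally: k × 40 + (4 − k) × 20.

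| Period | k | Literal reading | Age rule | Excess per cycle |
|---|---|---|---|---|
| Cycles 1-2 | 4 | 4×40 = 160 | 80 | 80 |
| Cycles 3-6 | 2 | 2×40 + 2×20 = 120 | 80 | 40 |
| Cycle 7 on | 1 | 40 + 3×20 = 100 | 80 | 20 |

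On each infusion day the ratio is 40/20 = 2. A patient who completes Cycles 1-2 receives 8 × (40 − 20) = 160 mg more under the literal reading (320 against 160 mg).

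**Dose intensity.** A patient over 75 given 20 mg weekly in Cycle 1 receives 80 mg. Against a planned 80 mg that is 100%; against a planned 160 mg it is 80/160 = 50%.

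**Does 20 mg suffice as pre-medication?** Appendix 2 lists "intravenous corticosteroid (dexamethasone 20 mg, methylprednisolone 100 mg, or equivalent dose of an intermediate-acting or long-acting corticosteroid". A 20 mg dose matches the dexamethasone figure there, so correcting the age rule does not take a patient below the Protocol's own pre-medication dose.

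**The case against.** The strongest reply is that the correct dose is easy to recover. The age rule stands one sentence earlier, Section 6.1.5 and Table 7.2 repeat it, and the infusion-day sentence can be read as setting only route, timing and dual role. On intent this is persuasive: it looks like a dropped parenthesis and not a competing dosing policy. It does not make the sentence correct. The sentence states a dose, words it as an instruction, and calls it the therapeutic dose.

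A second reply is that the general dose is only recommended, with dexamethasone given according to standard practice. That softens the general rule, but the infusion-day sentence does not use that language.

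Three stronger readings are tempting, and the documents do not support them:

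- A reader might add the SAP statements and set nine mentions of 20 mg against one of 40 mg. Four of the nine are in an older SAP from which sites do not dose. The comparison that counts is one sentence against five in the current Protocol.
- A reader might infer that patients were overdosed or harmed. The documents give neither the number of patients over 75 nor how sites read the sentence, and nothing in them says that renal impairment changes dexamethasone dosing. The Protocol gives 40 mg to patients aged 75 or younger under the same renal criterion.
- A reader might infer that the sentence should also carry the reduced levels of Section 6.1.5. Levels of 12 and 8 mg (over 75) and 10 mg (75 or younger) fall below the 20 mg in Appendix 2, while the same sentence bars any other corticosteroid pre-medication. Adding them alone would leave those patients with less cover against infusion reactions, which Section 6.1.4 says occur in about half of patients.

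**Conclusion.** The infusion-day sentence in Section 6.1.4 is wrong as written and should be corrected. For a patient over 75 whose site follows it literally, the dose doubles on each infusion day. The excess per cycle is largest in Cycles 1-2, when every dexamethasone day is affected, and shrinks as infusions become less frequent. These amounts assume the starting dose, full attendance, and 20 mg on days without an infusion. They describe what the text would produce, not what any site is known to have done.

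The intended dose is almost certainly 20 mg. This is a dosing and safety inconsistency: the PFS analysis and the sample size do not depend on it.

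**What to change.** In the infusion-day sentence of Section 6.1.4, insert a parenthesis directly after the 40 mg figure giving 20 mg for patients over 75 years of age. Leave the route, timing and dual-role wording unchanged. Do not add the Section 6.1.5 reduced levels to this sentence unless the same amendment allows supplementary corticosteroid pre-medication for levels below 20 mg; that is a separate clinical decision for the sponsor.

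The cost is one parenthesis, the ethics committee and competent authority review that Section 13.2 requires for any amendment, and a letter to sites. Data collection, the sample size and the PFS analysis do not change, and the SAP's dosing text already gives 20 mg for this group.

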## 6.1.5 Dose Adjustments/Modifications/Delays

### ➤ Daratumumab

No dose adjustment or modification is permitted for daratumumab. Infusion reactions may lead to the interruption of IV daratumumab administration. Pre-infusion medications should be administered to reduce the risk of infusion-related reactions (IRRs) prior to treatment.

For IRRs of any grade/severity, immediately interrupt daratumumab infusion and manage symptoms. The management of IRRs may further require reduction in the rate of infusion, or treatment discontinuation of daratumumab as outlined below.

- Grade 1-2 (mild to moderate): Once the patient's condition is stable, the infusion should be resumed at no more than half the rate at which the IRR occurred. If the patient does not experience any further IRR symptoms, infusion rate escalation may be resumed at increments and intervals as clinically appropriate up to the maximum rate of 200 mL/hour.

- Grade 3 (severe): Once reaction symptoms resolve, restarting of the infusion may be considered at no more than half the rate at which the reaction occurred. If the patient does not experience additional symptoms, infusion rate escalation may be resumed at increments and intervals as appropriate. The procedure above should be repeated in the event of recurrence of Grade 3 symptoms. Permanently discontinue daratumumab if the patient experiences a  $\geq$  Grade 3 infusion-related symptom at the subsequent infusion.
- Grade 4 (life threatening): Permanently discontinue daratumumab treatment.

See [Appendix 2](#) for further guidelines concerning the administration of daratumumab.

See the Summary of Product Characteristics for more details about daratumumab

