### **Daratumumab Toxicity Management**

In the event of one of the following toxicities the infusion should be held to allow for recovery. The criteria for a dose delay are:

- Grade 4 hematologic toxicity, except for Grade 4 lymphopenia
- Grade 3 or higher thrombocytopenia
- Febrile neutropenia
- Neutropenia with infection, of any grade
- Grade 3 or higher non-hematologic toxicities with the following exceptions:
  - Grade 3 nausea that responds to antiemetic treatment within 7 days
  - Grade 3 vomiting that responds to antiemetic treatment within 7 days
  - Grade 3 diarrhea that responds to antidiarrheal treatment within 7 days
  - Grade 3 fatigue that was present at baseline or that lasts for  $<7$  days after the last administration of daratumumab
  - Grade 3 asthenia that was present at baseline or that lasts for  $<7$  days after the last administration of daratumumab

Daratumumab treatment should be resumed when the toxicity has resolved to Grade 2. If daratumumab administration does not commence within the prespecified window ([Table 6.1](#)) of the scheduled administration date, then the dose will be considered a missed dose. Administration may resume at the next planned dosing date. A missed dose will not be made up.

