### 7.3.3 Rescue Medications, Treatments and Procedures

See [Appendix 2](#) for guidelines for managing infusion-related reactions.

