### Management of infusion-related reactions

Pre-infusion medications should be administered to reduce the risk of infusion-related reactions (IRRs) prior to treatment with DARZALEX.

For IRRs of any grade/severity, immediately interrupt the DARZALEX infusion and manage symptoms.

Management of IRRs may further require reduction in the rate of infusion, or treatment discontinuation of DARZALEX as outlined below.

- Grade 1-2 (mild to moderate): Once the patient's condition is stable, the infusion should be resumed at no more than half the rate at which the IRR occurred. If the patient does not experience any further IRR symptoms, infusion rate escalation may be resumed at increments and intervals as clinically appropriate up to a maximum rate of 200 mL/hour (Table above).
- Grade 3 (severe): If the intensity of the IRR decreases to Grade 2 or lower, restarting of the infusion may be considered at no more than half the rate at which the reaction occurred. If the patient does not experience additional symptoms, infusion rate escalation may be resumed at increments and intervals as appropriate (Table above). The procedure above should be repeated in the event of recurrence of Grade 3 symptoms. Permanently discontinue DARZALEX if the patient experiences a  $\geq$  Grade 3 infusion-related symptom at the subsequent infusion.
- Grade 4 (life threatening): Permanently discontinue DARZALEX treatment.

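### Section 6.1.5 and Appendix 2 of the Protocol give different conditions for restarting an infusion after a Grade 3 reaction, and neither is said to govern

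*Protocol*

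**What the plan says.** Protocol section 6.1.5, under Daratumumab, sets the restart condition for a Grade 3 reaction: "Once reaction symptoms resolve, restarting of the infusion may be considered at no more than half the rate at which the reaction occurred". No grade is attached to the word *resolve*.

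Appendix 2, under the management of infusion-related reactions, sets a condition for the same event: "If the intensity of the IRR decreases to Grade 2 or lower, restarting of the infusion may be considered", again at no more than half the rate at which the reaction occurred.

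The cross-references lead to both texts. Section 6.1.5 sends the reader to Appendix 2 "for further guidelines concerning the administration of daratumumab". Section 7.3.3 sends the reader to Appendix 2 alone "for guidelines for managing infusion-related reactions". Neither says which text prevails.

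Two nearby rules bear on the point:

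- Also within 6.1.5, the toxicity-management text on dose delays states: "Daratumumab treatment should be resumed when the toxicity has resolved to Grade 2".
- Section 5.3.1 makes three recurrences of a Grade 3 or higher reaction during one infusion a reason for mandatory discontinuation, and refers to Appendix 2.

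**The concern.** These are instructions for staff at the infusion chair, who can reach either text by following the Protocol's own references. If a reaction falls from Grade 3 to Grade 2 and symptoms remain, staff working from Appendix 2 may consider restarting. Staff working from section 6.1.5 would, on its plain wording, wait.

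Four things are at stake:

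- how that patient is handled;
- how long the infusion stays interrupted;
- whether a further Grade 3 reaction can occur within the same infusion, since a recurrence needs a restart and the number of recurrences feeds the stopping rule in section 5.3.1;
- whether the restart is a protocol deviation. Section 14.3 counts any noncompliance with the Protocol as a deviation, so one and the same restart could be recorded as compliant under Appendix 2 and as a deviation under 6.1.5.

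**Working it through.** The plan states no figure on this point, so the main check is a comparison of the two texts.

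**Step 1: what is common.** Both Grade 3 paragraphs cap the restart rate at half, allow re-escalation if no further symptoms appear, repeat the procedure if Grade 3 symptoms recur, and end treatment for a Grade 3 or higher symptom at the next infusion. The restart condition is the substantive difference.

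**Step 2: where the conditions diverge.** Take each state that can follow a Grade 3 reaction and ask whether a restart may be considered.

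| State of the reaction | Section 6.1.5, plain reading | Appendix 2 |
|---|---|---|
| Still Grade 3 | No | No |
| Eased to Grade 2, symptoms present | No | Yes |
| Eased to Grade 1, symptoms present | No | Yes |
| Symptoms gone | Yes | Yes |

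The texts disagree in the two middle rows only.

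**Step 3: does another passage settle it?** Sections 6.1.5 and 7.3.3 both point to Appendix 2 without ranking the texts. The Grade 2 wording in the toxicity-management part of 6.1.5 governs resuming treatment after a scheduled dose has been held, not restarting an interrupted infusion. The SAP does not address the management of infusion reactions.

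**Step 4: the link to section 5.3.1.** That section ends treatment after three recurrences in one infusion. The Grade 3 paragraphs in 6.1.5 and Appendix 2 tell sites to repeat the restart procedure on recurrence and state no limit on the number of repeats. Section 5.3.1 cites Appendix 2, but the count does not appear there.

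**Step 5: size.** The documents give no rate for reactions that ease to Grade 1 or 2 with symptoms persisting when a restart is considered. An upper bound needs an assumed Grade 3 rate. Section 1.2 quotes 5% for daratumumab with lenalidomide and dexamethasone, read here as a share of patients.

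- Expected patients with any Grade 3 reaction: 0.05 × 38 = 1.9.
- The Amendment 1 entry in the amendment log cites 6% across monotherapy and combination studies: 0.06 × 38 = 2.28.
- If a fraction f of patients with a Grade 3 reaction reaches the state where the texts differ, the expected number is 1.9 × f at the 5% rate. It runs from 0 (f = 0) through 0.95 (f = 0.5) to 1.9 (f = 1). The documents do not give f.

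**The case against.** The strongest reply is that the two texts are not opposed orders. Each says only that a restart may be considered, so the decision stays with the investigator, and a site that waits for full resolution complies with both. This stands. The texts are permissive conditions with different thresholds.

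A second reply is that *resolve* is undefined and that 6.1.5 elsewhere uses the word with a grade endpoint, so Appendix 2 could be read as the detail behind a short statement. That reading is available, but the text does not establish it. The other passage deals with held doses. It also shows that the authors name a grade when they mean partial resolution, and the Grade 3 restart sentence names none.

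Three stronger readings are tempting, and the documents do not support them:

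- **Reaction and discontinuation rates.** A reader might infer that these become inconsistent across sites. The first reaction precedes any restart, so its rate cannot depend on the restart condition. The discontinuation wording in 6.1.5 and Appendix 2 is the same. Only the count in section 5.3.1 could be reached by way of more restarts. Data from all sites are pooled, and no comparison between sites is planned.
- **Probability of conflict.** A reader might take 1 − 0.95^38 = 0.86 as the chance that the conflict arises at least once. It is the chance of at least one patient with any Grade 3 reaction, at a rate borrowed from another regimen in patients with a median of one prior line. This trial requires at least two prior lines and severe renal impairment or dialysis.
- **Per Protocol Set.** A reader might infer that patients would drop out of it. That needs the restart to be classed as a major deviation, and neither document lists which deviations are major.

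**Conclusion.** The inconsistency is real and narrow. For a Grade 3 reaction that has eased to Grade 1 or 2 with symptoms persisting, Appendix 2 lets a restart be considered and section 6.1.5, on its plain reading, does not. Nothing in either document says which text governs. The conclusion rests on reading *resolve* without a grade as full resolution. If that reading is rejected, an undefined term in a safety instruction remains.

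The number affected is unknown. Assuming the 5% rate, about 2 of 38 patients is an upper bound on the expected number, because it counts every patient with a Grade 3 reaction. The case therefore rests on clear instructions and consistent deviation recording, not on a measurable effect on results. PFS as the primary endpoint, alpha and sample size are untouched. The correction should be made, at modest priority.

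**What to change.** The sponsor should reconcile the Grade 3 paragraphs in section 6.1.5 and Appendix 2 so that one restart criterion appears in both, with any term such as *resolve* defined. In the same change, the within-infusion recurrence rule in section 5.3.1 should be reconciled with the instruction in 6.1.5 and Appendix 2 to repeat the procedure, so that all three places agree. Which criterion and which limit apply is a clinical decision for the sponsor; this review proposes neither.

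The cost is about a sentence in each affected place at the next amendment, plus a notice to sites. No analysis, sample-size or SAP change follows from it.
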